All dichotomous efficacy and	Composite responder	Proportion of responders where	No, only data up until discontinuation	Participants who start restricted medication** or discontinue study	Endpoint definition effectively

Endpoints	Estimand strategy	Estimand description	Use post-discontinuation data?	Imputation	Possible analysis method (estimator)
PRO endpoints		participants who start restricted medication or discontinue study intervention are considered treatment failures	is required to define endpoint	intervention are defined as nonresponders	gives complete data

*Note: No actual imputed value per participant, mixed model used to derive result at treatment group level.

** Restricted medications include prohibited medications (Section 6.5.2) and permitted medications above the allowable dose range (Section 6.5.1).

Any change to the data analysis methods described in the protocol will require an amendment only if the change affects a principal feature of the protocol. Any other change to the data analysis methods described in the protocol, and the justification for making the change, will be described in the SAP and the clinical study report (CSR). Additional exploratory analyses of the data will be conducted as deemed appropriate.

The SAP will be finalized prior to unblinding. It will include a more technical and detailed description of the statistical analyses described in this section.

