In cases when a participant is unable to come to the site to receive study intervention during normal on-site visit, the site should work with the sponsor to determine appropriate actions to administer the study intervention to the participant. This may include administration of study intervention to the participant during a mobile health visit, provided these requirements are met prior to administration of intervention:

1. sponsor approves the alternative method to on-site administration, taking local regulatory requirements into consideration
2. participant consent must include provision of any personal information

3. delivery of intervention does not compromise treatment blinding and ensures product integrity. The existing protocol requirements for product accountability remain unchanged
4. investigator/sponsor provides oversight of the transport process to ensure accountability and product quality (i.e., storage conditions and intact packaging upon receipt)
5. only authorized study staff or designee may supply or administer study intervention, and
6. resuscitation equipment, emergency drugs, and appropriately trained medical staff must be available during the infusion and for at least 1 hour after the completion of the infusion, in case of hypersensitivity or infusion site reactions.

Concomitant medications may be recorded during a remote visit.

Study Assessments and Procedures

Remote visits to complete appropriate assessments are acceptable. Site staff should capture the visit location and method with a specific explanation for any possible data missing in the source document and eCRF.

Visit Windows

Every effort should be made for the participant to return to on-site visits as soon as reasonably possible, while ensuring the safety of the participant and investigational site staff.

Except for Visits 6 and 7, flexibility in visit windows can be considered following consultation with and prior approval by the sponsor.

Efficacy Assessments

Conduct or review of participant-reported outcomes may be completed during a telehealth visit. These activities and health care professional RA evaluations, including assessments of the disease activity by a blinded assessor, may be conducted during a mobile health visit.

Safety Assessments

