The baseline period is defined as Visit 1 through pre-dose Visit 2. The Double-blind Treatment Period starts after the first injection of study treatment at Visit 2 (Week 0) and ends on the date of Visit 6 (Week 12) or the early discontinuation visit. The Period 2 starts after the date of Visit 6 (Week 12) or the early discontinuation visit and lasts up to 24 weeks following the last injection of study treatment. Additional follow-up beyond 24 weeks may be deemed necessary and, if so, any data collected will be considered as part of Period 2.

Unless otherwise specified, baseline for the Treatment Period is defined as the last non-missing assessment on or prior to the date of the first injection of study treatment, scheduled to be given at the end of Visit 2. Any assessment collected after the first injection through the date of the Week 12 or early discontinuation visit is defined as post-baseline for the Treatment Period.

Data collected at early discontinuation visits will be mapped to the next planned visit number for that patient. For by-visit summaries, only visits in which a measure was scheduled to be collected will be summarized.

Summaries of safety data collected during Period 2 will be presented separately. Unless otherwise specified, follow-up baseline is defined as the last non-missing assessment on or prior to the date of Week 12 or the date of the early discontinuation visit.

Change from baseline will be calculated as the post-baseline value minus the baseline value. Percent change from baseline is defined as $(100 \times (\text{post-baseline} - \text{baseline}) / \text{baseline})$. If all baseline values are missing for a particular variable, the change from baseline and percent change from baseline will not be calculated.

The statistical analyses of efficacy, health outcomes, and safety measures will be performed using SAS Version 9.4 or higher. Lilly will be responsible for conducting analyses.

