4.4.1.2. Main analytical approach

4.4.1.2.1 ACR20

The frequency and percentage of patients achieving ACR20 response will be summarized by treatment arm at each post-baseline visit. A logistic regression model will be used to test the treatment difference of each LY dose versus placebo at each post-baseline visit with treatment group, baseline disease activity, and previous RA therapy population as model covariates. Baseline DAS28-CRP score will be used as the baseline variable. NRI as described in Section 4.1 will be used to impute missing data for ACR20 in patients who were Week 12 non-responders or who discontinued prior to Week 12.

The Kaplan-Meier estimator will be used to summarize time to ACR20 response over 12 weeks and a plot by treatment arm will be presented. Week 12 non-responders will be censored on the date of the Week 12 visit. All patients ongoing at Week 12 and who have not yet responded will be censored on the date of the Week 12 visit. A Cox proportional hazards model will be used to test the treatment comparison between each LY dose and placebo in time to ACR20 response over 12 weeks.

For participants who discontinue study intervention and/or receive rescue therapy, post-discontinuation or post-rescue observations will not be included.

Subjects with ACR20 response will also be listed.

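### Time to ACR20/50/70: censoring on each participant's own Week 12 visit date distorts the end of the Kaplan-Meier curve, and the status of participants who stop drug and the Cox covariates are not stated

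*SAP*

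**What the plan says.** SAP 4.4.1.2.1 adds a time-to-response analysis to the by-visit ACR20 proportions: "The Kaplan-Meier estimator will be used to summarize time to ACR20 response over 12 weeks and a plot by treatment arm will be presented". Two sentences set the censoring: "Week 12 non-responders will be censored on the date of the Week 12 visit" and "All patients ongoing at Week 12 and who have not yet responded will be censored on the date of the Week 12 visit". The test is given as: "A Cox proportional hazards model will be used to test the treatment comparison between each LY dose and placebo". No covariates and no method for ties are named.

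For participants who stop drug or are rescued, the section says only: "For participants who discontinue study intervention and/or receive rescue therapy, post-discontinuation or post-rescue observations will not be included". It gives them neither a censoring date nor a failure status in the time-to-response analysis.

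Other relevant text:
- The Schedule of Activities (Protocol 1.3) sets the Week 12 visit at day 84 ± 7. Protocol 10.8 does not widen this in exceptional circumstances: "Except for Visits 6 and 7, flexibility in visit windows can be considered following consultation with and prior approval by the sponsor".
- The non-responder imputation (NRI) rule in SAP 4.1 counts anyone who permanently stops study drug as a non-responder. For dichotomous endpoints, Protocol 9.4.1 states that "participants who start restricted medication or discontinue study intervention are considered treatment failures".
- The ACR20 logistic model in the same section adjusts for baseline DAS28-CRP and previous RA therapy population. The SAP's other Cox model, for time to anti-drug antibodies (SAP 4.6.4.4), includes the randomisation stratum.
- SAP 4.4.1.2.2 applies the ACR20 methods to ACR50 and ACR70 by citing a Section 16.1.3.1, which this SAP does not contain.

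**The concern.** During the double-blind period, response is seen only at Weeks 2, 4, 8 and 12. Everyone still without a response at Week 12 either responds or is censored on the day they attend, and those days can differ by up to two weeks. The Kaplan-Meier estimator treats a non-responder seen on day 78 as someone whose status on day 90 is unknown. In fact that person has completed the last scheduled assessment of the period. Each later Week 12 response is then divided by a shrinking risk set, so the last part of the curve depends on the order of attendance.

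The missing rule for stoppers leaves a second choice to the programmer. Excluding later observations leads naturally to censoring at stopping. That would assume stoppers go on to respond at the same rate as those who remain, whereas the ACR proportions count them as failures.

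At stake is the reading of a planned plot and test for each dose, on three responder endpoints, with about 20 participants in two of the three arms. SAP 4.4.1.3 plans no sensitivity analysis that would expose the effect.

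**Working it through.** **The plan's own figures.** Neither document gives a figure for ACR20 or for time to response. The only design figure is power above 80% for the primary endpoint, and it reproduces. The noncentrality is 1.05 / (1.25 × √(1/40 + 1/20)) = 3.07, which on 58 df gives 85.5%. Nothing below changes it.

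**Own-date censoring by hand, no stoppers.** Take 20 participants. Six respond by Week 8, 14 attend Week 12 on days 78 to 91 (one a day), and two of those respond. True ever-response is 8/20 = 40%. After Week 8, S = 14/20 = 0.70.

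| Days of the two Week 12 responses | Response read at day 84 | Response at end of curve |
|---|---|---|
| 78, 79 | 1 − 0.70 × 13/14 × 12/13 = 40.0% | 40.0% |
| 82, 87 | 1 − 0.70 × 9/10 = 37.0% | 1 − 0.70 × 9/10 × 4/5 = 49.6% |
| 89, 90 | 1 − 0.70 = 30.0% | 1 − 0.70 × 2/3 × 1/2 = 76.7% |
| 84, 91 | 1 − 0.70 × 7/8 = 38.8% | 1 − 0.70 × 7/8 × 0/1 = 100% |

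The responses are the same in every row; only the attendance order differs. With all 14 visits on day 84, the estimate is 1 − 0.70 × 12/14 = 40.0%.

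**Simulation, no stoppers.** Response rates and visit spread are assumptions; only the ±7-day window is documented. First-response probabilities at Weeks 2/4/8/12 were set to .10/.08/.08/.06 for placebo (n=20, sum 32%) and .15/.15/.15/.10 for 700 mg (n=40, sum 55%).

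| Visit spread | End of curve, n=20 | End of curve, n=40 |
|---|---|---|
| nominal days | 32% | 55% |
| ±2 days | 39% | 65% |
| ±3 days | 40% | 67% |
| ±7 days | 42% | 70% |

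At ±7 days the excess is 42 − 32 = 10 points and 70 − 55 = 15 points. The curve reaches 100% in about 5% (n=20) and 9% (n=40) of runs. Read at day 84 with the same spread, it gives about 30% and 52%, which is 2 to 3 points too low, because visits on days 85 to 91 are not yet counted.

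A second set of assumed rates (true response 33% and 58%) gave 47–49% and 74–75% at day 91, and 30–31% and 54% at day 84. The signs are the same, with a somewhat larger excess at the end of the curve.

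**Stoppers censored at stopping, nominal visit days.** Take 20 participants: four stop at day 40, six respond at Week 8 and two at Week 12. Then 1 − (10/16)(8/10) = 50.0%, against 8/20 = 40.0% if stoppers stay in the denominator. With two stoppers, 1 − (12/18)(10/12) = 44.4%. In simulation with the second set of rates, the excess at 5/10/20% stopping was 0.9/1.8/3.7 points (n=20) and 1.5/2.9/5.9 points (n=40).

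**After the fix.** With time in nominal weeks and every participant without a response, stoppers included, kept at risk through Week 12, the hand examples return 8/20 = 40.0%.

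**The treatment test.** Under the first set of rates, an unadjusted log-rank test (the score-test analogue of the Cox comparison) had type I error of 4.0% with nominal visits and 5.0% at ±7 days. Power was 34.3% and 35.1%. Own-date censoring did not visibly harm the comparison.

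**The case against.** The strongest reply is that this is an extra analysis in a proof-of-concept trial. Time to ACR20 is not a listed endpoint in either document and has no estimand of its own. That stands, and it sets the severity.

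Several stronger readings are tempting, and the documents do not support them:

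- **A reader might infer that the curve overstates response in every arm and inflates the gap between arms.** This holds only towards the end of the curve, where the gap at ±7 days is 70 − 42 = 28 points against a true 55 − 32 = 23. At day 84, a natural reading of 12 weeks, response is slightly understated and the gap is about 22 points. The SAP does not say on which day the curve is read.
- **A reader might compare the curve with the Week 12 NRI rate and call any excess bias.** The curve estimates ever responding; the NRI proportion is response at a visit. Someone who responds at Week 4 and loses response counts in the first but not in the second, so the two can differ with perfect visit dates.
- **A reader might say the section contradicts the composite estimand.** Protocol 9.4.1 writes that strategy for dichotomous endpoints. Censoring at stopping is also an inference from silence. The NRI rule could place stoppers among the Week 12 non-responders, although they may have no Week 12 visit date. SAP 4.1 complicates this further: "Data collected at early discontinuation visits will be mapped to the next planned visit number for that patient". The section leaves a rule unstated, which falls short of a contradiction.
- **A reader might conclude that the Cox model is unadjusted.** The section is silent, and SAP 4.1 allows efficacy models to include baseline disease activity and previous RA therapy population.

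The size of the stopping effect is also open. Protocol 7.2 expects discontinuation to be uncommon, and at 5% stopping the excess is about 1 to 1.5 points.

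**Conclusion.** The point holds as a minor one. Followed exactly, own-date censoring makes the end of the Kaplan-Meier curve overstate cumulative response, by about 10 points (n=20) and 15 points (n=40) when visits spread over the full ±7 days. At day 84 the same curve understates response by about 2 to 3 points. The effect is zero when visits fall on nominal days and nobody stops drug. These sizes rest on assumed response rates and visit spread; the mechanism follows from the SAP wording and the documented window.

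Two gaps sit beside it. Participants who stop drug or are rescued have no stated status. Censoring them at stopping would be inconsistent with the NRI handling of the ACR proportions and would add about 1 to 6 points at 5–20% stopping. The Cox covariates are not named, although the ACR20 logistic model and the SAP's other Cox model both adjust for previous RA therapy population.

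The primary analysis and the ACR20/50/70 logistic tests are unaffected. Harm to the Cox comparison has not been shown.

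**What to change.** In SAP 4.4.1.2.1, and in 4.4.1.2.2 with its cross-reference corrected:

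1. Define time to response as the nominal visit week (2, 4, 8 or 12), with all participants without a response censored at Week 12. This also settles where the curve is read.
2. State that participants who stop drug or start restricted medication without a prior response remain non-responders, censored at Week 12.
3. Fit the Cox model adjusted for baseline DAS28-CRP and previous RA therapy population, with a stated method for ties. With only four possible event times, ties will be heavy.
4. Label the plotted quantity as cumulative first response, so that it is not read as the Week 12 NRI rate.

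The cost is SAP wording and a small programming change, with no new data. It should be settled before unblinding.

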4.1. General Considerations

The independent variable, previous RA therapy population, is defined as only csDMARD experienced or bDMARD/tsDMARD experienced participants. Unless otherwise indicated in the statistical analysis plan (SAP), the analyses will be conducted as follows:

Analysis for	Description
Primary and secondary endpoint analyses comparing LY3462817 to placebo	Tested at a 2-sided level of 0.05 for frequentist analyses
Adjustments for multiplicity	None to be performed
Baseline	Defined as the last available value before the first dose of study intervention for both efficacy and safety analyses. In most cases, this value will be what is recorded at the randomization visit (Visit 2).
Change from baseline	Will be calculated as the visit value of interest minus the baseline value.
Efficacy and patient-reported outcome (PRO) analysis	Analysis models may contain the independent variables such as treatment group, baseline disease activity, and previous RA therapy population. Endpoint analyses will use the FAS unless otherwise specified.
Dichotomous responder endpoints	Missing data will be imputed using the nonresponder imputation (NRI) method. Will be analyzed using a logistic regression model with treatment group, baseline disease activity, and previous RA therapy population as model covariates.
NRI analysis	Participants will be considered nonresponders if: 
 • they do not meet all the clinical response criteria • they are noncompliant with concomitant medication rules

	
 • they permanently discontinue study intervention at any time before the end of the treatment period for any reason, or • they are randomized and do not have at least 1 postbaseline observation.
Continuous efficacy endpoints	
Mixed-effects model for repeated measures (MMRM) will be used.
 
The MMRM model will include treatment, strata (previous RA therapy population), baseline value, visit, treatment-by-visit interaction in the model as fixed factors, and patient as a random factor.
 
An unstructured covariance matrix will be used to model the within-subject errors. If this analysis fails to converge, other structures will be tested (in this order: Toeplitz, Autoregressive with heterogeneity, and compound symmetry.).
 
The Kenward-Roger approximation will be used to estimate denominator degrees of freedom. Significance tests will be based on least squares means and Type III tests.

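### The time-to-ACR20 analysis in SAP 4.4.1.2.1 does not define its event, and its two censoring sentences disagree for early responders who are not responders at Week 12

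*SAP*

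**What the plan says.** SAP 4.4.1.2.1 (ACR20) first covers response by visit: "The frequency and percentage of patients achieving ACR20 response will be summarized by treatment arm at each post-baseline visit", with logistic regression and nonresponder imputation (NRI). It then adds a time-to-event analysis: "The Kaplan-Meier estimator will be used to summarize time to ACR20 response over 12 weeks and a plot by treatment arm will be presented". Two consecutive sentences set the censoring:

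- Sentence 1: "Week 12 non-responders will be censored on the date of the Week 12 visit".
- Sentence 2: "All patients ongoing at Week 12 and who have not yet responded will be censored on the date of the Week 12 visit".

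The resulting event status feeds a test: "A Cox proportional hazards model will be used to test the treatment comparison between each LY dose and placebo in time to ACR20 response".

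The section does not say whether the event is the first response or a response still present at Week 12, and it does not define a Week 12 non-responder. The term also appears one paragraph earlier, where NRI applies to "patients who were Week 12 non-responders or who discontinued prior to Week 12". SAP 4.4.1.2.2 asks for similar analyses of ACR50 and ACR70, citing a Section 16.1.3.1 that this SAP does not contain. The protocol describes no time-to-response analysis that could settle the point.

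**The concern.** The ACR20 components are collected at Weeks 2, 4, 8 and 12 (Protocol 1.3, Schedule of Activities), so a participant can gain a response and lose it again. Sentence 2 implies that anyone who has already responded is an event. Sentence 1, taken literally, censors everyone who is not a responder at Week 12 and makes no exception for an earlier response.

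Under sentence 1, a Week 4 response counts only if the participant is also a responder at Week 12. The participant is kept in the risk set for eight weeks after responding because of what a later visit showed. That is no longer time to first response. Both rules can be taken from the same paragraph, so the choice could be made after unblinding. Protocol 9.5 requires the SAP to be final before any unblinding in order to prevent choices of that kind.

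**Working it through.** **Stated figure.** The documents give no event count, hazard ratio or power for time to ACR20, so there is nothing to reproduce. The core check is logical.

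**Step 1: apply each sentence to response patterns at Weeks 2/4/8/12.**

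| Pattern | Sentence 1, literal | Sentence 2 |
|---|---|---|
| no/no/no/no | censored, Week 12 | censored, Week 12 |
| no/yes/yes/yes | event, Week 4 | event, Week 4 |
| no/no/no/yes | event, Week 12 | event, Week 12 |
| no/yes/yes/no | censored, Week 12 | event, Week 4 |

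The sentences diverge only for participants who respond early and are not responders at Week 12.

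**Step 2: where the curve ends.** With no dropout, all censoring falls at Week 12. The Kaplan-Meier incidence at Week 12 is then the proportion with an event. That is the Week 12 response rate under sentence 1 and the ever-response rate under sentence 2.

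**Step 3: size, on assumed rates.** From the documents: 40 participants on 700 mg and 20 on placebo (SAP 5), and two-sided 0.05 (SAP 4.1). Assumed: ACR20 at Weeks 2/4/8/12, a latent normal variable per participant with correlation 0.5 to 0.85, and no dropout. Placebo is 15/22/28/30% in both sets.

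- Set A: LY 25/38/48/55%, correlation ρ^(lag in weeks/4).
- Set B: LY 20/35/47/52%, equal correlation between all visits.

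| | Sentence 1 | Sentence 2 |
|---|---|---|
| Set A, placebo curve at Week 12 | 30% | 40% to 53% |
| Set A, LY curve at Week 12 | 55% | 64% to 77% |
| Set A, hazard ratio | 2.2 to 2.4 | 1.8 to 2.0 |
| Set B, placebo curve at Week 12 | 30% to 31% | 39% to 51% |
| Set B, LY curve at Week 12 | 50% to 53% | 59% to 73% |
| Set B, hazard ratio | 1.9 to 2.1 | 1.7 to 1.8 |

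In Set B about 2 to 4 of 20 placebo and 3 to 8 of 40 LY participants change status. Those are 23% to 39% of placebo ever-responders and 14% to 28% of LY ever-responders.

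**Step 4: against sampling error.**

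- Placebo curve: SE = sqrt(0.30 × 0.70 / 20) = 0.102. A shift of 10 to 23 points is about one to a little over two standard errors.
- Hazard ratio, Set A: events under sentence 1 are 0.55 × 40 = 22 and 0.30 × 20 = 6, so SE(log HR) ≈ sqrt(1/22 + 1/6) = 0.46. The shift lies between ln(2.3/2.0) = 0.14 and ln(2.4/1.8) = 0.29, or 0.3 to 0.6 SE.
- With the largest sentence 2 counts (0.77 × 40 ≈ 31 and 0.53 × 20 ≈ 11), SE ≈ sqrt(1/31 + 1/11) = 0.35, and 0.29/0.35 = 0.8. The shift is still below one.

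**Step 5: test behaviour (Set B, log-rank, 3,000 simulated trials per scenario).**

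- With equal arms, rejection is 5.1% to 5.5% under sentence 1 and 4.8% to 5.5% under sentence 2.
- Under the assumed effect, rejection is 33% to 35% against 30% to 32%. The two rules reach different decisions in 17% to 26% of trials.

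**The case against.** The strongest defence is that, in a time-to-event paragraph, a Week 12 non-responder simply means someone with no response by Week 12. Both sentences then agree and early responders stay events. That reading is plausible. The reply that it would make sentence 2 redundant carries little weight, because this SAP repeats itself elsewhere (SAP 4.3.2 excludes post-discontinuation data twice). Sentence 1 might also have been meant for nonresponders who are no longer ongoing, since NRI applies if "they permanently discontinue study intervention at any time before the end of the treatment period for any reason". However, the NRI sentence lists discontinuers separately, and they may have no Week 12 visit on which to be censored. Its own use of the term, a group in which to "impute missing data for ACR20 in patients who were Week 12 non-responders or who discontinued prior to Week 12", points to status at Week 12, though it is loosely drafted itself. The benign reading may be what was intended, but it is not stated.

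The second defence is that little depends on this. Time to ACR20 is not a listed endpoint in the protocol or in SAP 4.4.1.1. The analysis is unpowered and unadjusted for multiplicity in a proof-of-concept trial. The listed endpoint, the proportion responding, has its own logistic model. All of this stands, and it limits the severity.

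A reader might infer that sentence 1 inflates the hazard ratio and so favours the drug. The documents do not support that. They give no rates, the ratio moves modestly and by an amount that depends on the assumptions, and simulated type I error is near 0.05 under both rules. Sentence 1 targets a different quantity, response still present at Week 12. A reader might also take the same text to govern ACR50 and ACR70. SAP 4.4.1.2.2 asks only for similar analyses, through a broken cross-reference.

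**Conclusion.** The point holds as a minor defect: the rule is wrong as written for an analysis of time to response. The event is undefined, and sentence 1, read literally and as the term is used in the preceding paragraph, lets a later visit decide whether an earlier response counts. This conclusion and the pattern table rest on the SAP text alone.

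The sizes rest wholly on assumed visit rates, within-person correlation and no dropout. Across the two sets, the placebo curve ends near 30% against about 40% to 53%, and the hazard ratio is about 1.9 to 2.4 against 1.7 to 2.0. The two readings can lead to different test decisions, but in a test with only about 30% to 35% power under the assumed effect. The primary endpoint and the Week 12 ACR20 proportion do not change.

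**What to change.** In SAP 4.4.1.2.1:

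1. Define the event as the first post-baseline visit with ACR20 response, regardless of status at later visits.
2. Delete sentence 1, or restrict it to participants with no ACR20 response at any post-baseline visit.
3. Keep sentence 2 with its condition that the participant is ongoing at Week 12. Do not extend Week 12 censoring to all never-responders, because early discontinuers may have no Week 12 visit. Their censoring date is a separate gap that needs its own rule.
4. In SAP 4.4.1.2.2, apply the same event definition to ACR50 and ACR70 and correct the cross-reference.

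Response at Week 12 itself is already tested by the logistic model, so no planned comparison is lost. The cost is SAP wording only, before unblinding, with no new data, visits or participants.
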